## **8.4 Laboratory Procedures**

All laboratory assessments will be performed locally at each center's laboratory by means of their established methods (using site specific laboratory normal values). Blood and urine samples should be taken using standard techniques and samples should be stored and shipped according to the laboratory guidelines.

## 85 Adverse Events

Adverse events will be recorded Starting on Day 1, immediately after study procedure has started and through to the End-of-Study (Week 24). Any adverse events experienced between signing the ICF and prior to administration of the study drug will be recorded in the medical history. See [Section 12](#) for more information pertaining to recording of adverse events.

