## STYLE TRIAL - PROTOCOL SUMMARY

Title	Subcutaneous Transplantation of Autologous Cell Enriched Adipose Tissue For Follicular Niche Stimulation in Early Stage Alopecia Androgenetica (STYLE): a Randomized, Blinded, Controlled Trial
Test Products	Celution® System (Celution Device, Celution Consumable Set and Celase) used for processing of Autologous Adipose Derived Regenerative Cells (ADRCs) combined with adipose tissue processed and purified with Puregraft® 50 System
Objective	The primary objective of this study is to evaluate the safety and feasibility of the Celution and Puregraft Systems in the processing and preparation of an autologous fat graft enriched with adipose-derived regenerative cells (ADRCs) in the treatment of early alopecia androgenetica.
Design	Prospective, Randomized, Controlled Safety and Feasibility Trial
Sample Size	70 patients (40 ADRC + adipose, 20 fat only control, 10 no-fat control )
Study Location	Up to (8) sites in the United States
Indication	Androgenic Alopecia (Androgenetica Alopecia, AGA)
Visit Schedule	Screening (Day -28 to Day -7), Pre-Procedure Day (Day -1)Procedure Day (Day 1), and follow up visits at weeks 1, 6, 12, 24 and 52 weeks
Treatment Arms	
Subjects will be randomized 2:2:2:1 to receive either 0.1ml/cm^2 scalp of autologous fat enriched with 0.5 x 10^6 ADRC/cm^2 scalp (n=20), 0.1 ml/cm^2 scalp of autologous fat enriched with 1.0 x 10^6 ADRCs/cm^2 scalp (n = 20), 0.1ml/cm^2 scalp of autologous fat enriched with a matching saline control (fat alone control; n=20), or 0.1 ml/cm^2 scalp of saline enriched with a matching dose of saline (no-fat control; n=10). In each subject, 40 square centimeters of scalp will be treated.
 
The study treatment will be delivered in the subcutaneous adipose layer of the scalp in via two separate injections – one of either 0.1ml/cm^2 scalp of adipose or saline followed by a second injection of ADRCs or saline per square centimeter of scalp.

Primary Endpoint	Safety & tolerability through 24 weeks
Secondary Endpoints	
 
• Trichograms (Hair Growth) at 24 weeks
 
• Trichograms (Hair Density) at 24 weeks
 
• Global photographs to assess scalp coverage at 24 weeks
 

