## **4.4 Study Duration**

Enrollment of subjects will occur over approximately 6 months. For each patient, the study duration will include a screening period of up to 28 days and a 52 week follow-up period. Therefore, the study duration is estimated to be 18 months.

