### **9.6 Post-injection Follow-up visits (Weeks 6, 12, 24, and 52)**

- Physical examination
- Vital Signs
- Assessment for Adverse Events

The following tests are to be performed:

- Subject questionnaire
- Global photography
- Hair Investigator Satisfaction Survey

A summary table of all follow up evaluations is outlined in [Appendix B: Schedule of Procedures](#)

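### Section 8.5 stops adverse event recording at Week 24 and calls that the end of the study, while follow-up and AE visits run to Week 52, so more than half of the safety follow-up may go unrecorded.

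*Combined protocol and SAP*

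**What the plan says.** Section 8.5 (Adverse Events) of Protocol Version B sets both ends of the recording period. Recording starts on Day 1 once the study procedure has begun and runs "through to the End-of-Study (Week 24").

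Other parts of the same version use a longer horizon:

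- **Section 4.4:** for each patient, "the study duration will include a screening period of up to 28 days and a 52 week follow-up period".
- **Protocol Summary:** the schedule lists "follow up visits at weeks 1, 6, 12, 24 and 52 weeks".
- **Section 9.6:** under the heading "Post-injection Follow-up visits (Weeks 6, 12, 24, and 52"), the tasks include "Assessment for Adverse Events".
- **Appendix A:** the Adverse Events row is marked at every visit from Day 1 through Week 52.
- **Section 12.1:** an adverse event is anything undesirable that happens over the course of the study.
- **Section 12.2:** events after the start of liposuction go on the AE eCRF, and SAEs and UADEs are reported within 24 hours. No end date is given for either.
- **Section 4.5.4:** AEs, SAEs and UADEs are the safety endpoints, with no time limit.

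The primary endpoint in Sections 4.5.1 and 11.3.1 is safety and tolerability through 24 weeks. Section 8.3 also ends eCRF recording of concomitant medications at 24 weeks after the procedure.

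**The concern.** The section that states when recording starts and stops contradicts the visit schedule. A site that follows Section 8.5 could close the AE form at Week 24, while a site that follows Section 9.6 or Appendix A would keep it open. Events in Weeks 24 to 52 could then be captured at some of the up to eight sites and not at others, and a low late event count could not be told apart from incomplete recording.

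The label adds a second problem. If Week 24 is the end of the study, it becomes arguable whether a serious event at Week 40 falls within the study for the reporting duty in Section 12.2.

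Safety is the trial's primary purpose, and the safety endpoints carry no 24-week limit. The part at risk is longer-term safety. The 24-week primary endpoint is not.

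**Working it through.** **1. Which end of study does the protocol's own duration imply?** Section 4.4 says that "Enrollment of subjects will occur over approximately 6 months" and concludes: "Therefore, the study duration is estimated to be 18 months". One month is 365.25 / 12 / 7 = 4.348 weeks.

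- With 52 weeks of follow-up: 6 + 52/4.348 = 17.96 months, within 0.2% of the stated 18.
- With 28 days of screening added: 6 + 56/4.348 = 18.88 months, 4.9% above 18. The stated figure appears to leave screening out.
- With follow-up ending at Week 24: 6 + 24/4.348 = 11.52 months.

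The stated duration is reproduced only with follow-up to Week 52.

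**2. Which rules end at Week 24 and which do not?**

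| Place (Version B) | Horizon for adverse events |
|---|---|
| Section 8.5 | Week 24, called the end of the study |
| Section 9.6 | Assessment at Weeks 6, 12, 24 and 52 |
| Appendix A, Adverse Events row | Day 1 through Week 52 |
| Sections 12.1 and 12.2 | Course of the study, no week given |
| Section 4.5.4 | No limit |

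Section 8.5 stands alone. Version A has the same conflict in its Sections 8.5 and 9.6 and its Appendix A. The Summary of Changes does not mention it, so it was carried through the amendment.

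**3. How much follow-up lies after the cut-off?**

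- Share of scheduled follow-up: (52 − 24)/52 = 28/52 = 53.8%. Section 8.5 as written covers 24/52 = 46.2%.
- Person-time for 70 subjects with no dropout: 70 × 28 = 1,960 of 70 × 52 = 3,640 person-weeks.

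**4. Does this depend on visit timing?** Appendix A allows 2 weeks either side of both visits. The share after the cut-off is (Week 52 visit − Week 24 visit) / Week 52 visit:

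| Week 24 visit at | Week 52 visit at 50 | at 52 | at 54 |
|---|---|---|---|
| 22 | 56.0% | 57.7% | 59.3% |
| 24 | 52.0% | 53.8% | 55.6% |
| 26 | 48.0% | 50.0% | 51.9% |

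Of these nine combinations, only the latest Week 24 visit with the earliest Week 52 visit falls below half. One other is exactly half.

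**The case against.** Section 8.5 is not the only rule. It sends the reader to Section 12, which sets no end date, and Section 9.6 and Appendix A plainly require assessment at Week 52. SAEs and UADEs have their own 24-hour route. Sites are trained and monitored, and the eCRF is not in the documents, so nothing shows that any form closes at Week 24. The 54% is calendar time, not lost information. No late-onset event is named among the delivery risks in Section 10.1.1, and the safety review triggers in Section 11.8.1 cover 7 and 14 days. Week 24 may have been chosen to match the primary endpoint. Changing one phrase would also leave the medication window at Week 24.

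Part of this stands. Loss and uneven capture are possibilities, and the likelier gap is in non-serious events. The rest does not remove the conflict:

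- The agreement of Sections 9.6 and 12 and Appendix A shows that Section 8.5 is the outlier, which supports correcting it.
- An analysis window of 24 weeks does not require collection to stop, and Section 8.5 says nothing about analysis. It names the end of the study.
- That label weakens the SAE route too, because the route is tied to events during the study.
- Medications stay in source documents throughout the study under Section 8.3, so late events could still be interpreted, though less conveniently.
- Exits after Week 24 are covered by Section 5.4, which asks for the procedures of the next scheduled visit.

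**Conclusion.** The concern holds. Section 8.5 contradicts Sections 4.4 and 9.6, Appendix A and the open-ended rules in Section 12. Followed literally, it drops non-serious adverse events over the last 28 of 52 weeks: 53.8% of scheduled follow-up, with a range of 48.0% to 59.3% across the allowed visit windows. The person-week figure assumes 70 subjects followed in full. How much would actually be lost depends on which section the sites and the eCRF follow, and the documents do not show this. The primary endpoint through 24 weeks is unaffected. The correction should be made, but it does not undermine the main analysis.

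**What to change.** In Section 8.5, move the end of adverse event recording to the end of study at Week 52, so that it agrees with Sections 4.4, 9.6 and 12 and with Appendix A. Confirm that the AE eCRF stays open to that visit. Keep the primary safety summary through Week 24 and add a second summary by arm for Weeks 24 to 52.

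In the same amendment, reconcile the Week 24 limit on eCRF medication recording in Section 8.3, so that late events have matching medication data.

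The cost is a short text change, one more safety table and a few more AE forms. Extending medication entry would add some eCRF work. The Week 52 visit and its adverse event assessment are already scheduled, so no visit is added and the primary analysis does not change.

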## 9 STUDY VISIT REQUIREMENTS

The Schedule of Procedures is outlined in [Appendix A](#).

### 9.1 Screening (within 28 to 7 days prior to procedure)

Subjects will undergo the following screening procedures:

- Written informed consent
- Inclusion and exclusion criteria evaluation
- Medical history
- Prior and concomitant medications
- Physical examination
- Laboratory Tests
  - CBC with Platelets
  - Electrolytes, alkaline phosphatase, bilirubin, AST, ALT, BUN, Creatinine
  - PTT, PT/INR
- Vital signs
- Pregnancy test (urine) for female patients of child-bearing potential
- Evaluation of suitability for fat tissue harvest and liposuction procedure(see *Section 9.3.3.1*)

The following tests are to be performed:

- Global Photography
- Trichogram with tattooing

### 9.2 Pre-Operative Procedures (Day -1; performed within 24 hours of the liposuction)

- Confirm inclusion/exclusion criteria
- Physical Examination
- Vital Signs
- Assessment for Adverse Events
- Concomitant Medications
  - Collect daily medication diary completed for 14 days immediately preceding visit
- Laboratory Tests
  - CBC with Platelets
  - Electrolytes, alkaline phosphatase, bilirubin, AST, ALT, BUN, Creatinine
  - PTT, PT/INR

- Pregnancy test (urine) for female patients of child-bearing potential

## 9.3 Procedure Day (Day 1)

### 9.3.1 Fat Harvest

#### 9.3.1.1 General requirements

- Fat harvest will be performed on the day of treatment as part of an independent, elective cosmetic liposuction.
- Fat harvest planning should include assessment of patients general health condition to undergo the procedure
- Standard tissue calipers or expert plastic surgical examination should be used to assess possible body sites for subcutaneous fat tissue. Patients should have greater than or equal to 2 cm of subcutaneous fat tissue available in each contemplated area to be suitable for liposuction
- Prepare up to 3 sites, including the preferred abdomen and flanks along with the inner and the outer thighs and the posterior and anterior thighs. To estimate harvestable fat from the harvest site the following guideline may be used: Estimated fat from the harvest site = volume of the site/8 = length of the marked skin x width of the marked skin x height (i.e. caliper skin-fold thickness) / 8. All patients who have inadequate fat deposits (i.e. < 200 ml of lipoaspirate from 3 bilateral sites) are to be excluded from the study. Any patient with an area of active skin infection in the site of lipoharvest will be excluded from the study.
- As noted elsewhere in this protocol, fat harvest should NOT be performed on patients who have received any anticoagulant within 1 hour of liposuction, substantial anticoagulation (e.g.: GIIb/IIIa inhibitor class drugs) within the two weeks prior to fat harvest, or who have an abnormal aPTT.
- Fat tissue should be obtained under sterile technique using local anesthesia with or without conscious sedation. General anesthesia should not be used.

#### 9.3.1.2 Fat Harvest Procedure

Fat harvest from small volume liposuction is a standard procedure practiced by trained physicians in a variety of settings and using a variety of techniques. However, a specific set of guidelines have been established for the collection of fat that can then be used for the optimized preparation of ADRCs. These guidelines, which are recommendations and not requirements, include the following;

- Syringe-based fat harvest is preferred.
- Use up to 32 cm long, 3-5 mm inner diameter Toomey cannula with a standard tip
- 60 mL Toomey syringes are used for tissue acquisition
- Use 14 gauge, up to 30 cm, blunt LAMIS infiltrator for tumescent fluid administration
- Symmetric fat removal is required keeping the overall area of aspiration as small as possible

- The abdominal region is the preferred site for fat harvest

1. Local anesthesia with or without conscious sedation; general anesthesia is not permitted for fat harvest
2. Using sterile technique, prepare up to 3 sites, including the preferred abdomen and flanks along with the inner and the outer thighs and the posterior and anterior thighs.
3. Make an approximately 0.5 cm stab skin incision
4. Infiltrate tumescent solution using a blunt LAMIS infiltrator and a volume ratio of 1:1 of tumescent solution to fat to be harvested

Tumescent fluid formula:

- 500 mL of Lactated Ringers solution
- 20 mL of 1% Lidocaine
- 1 mg of epinephrine

5. To sufficiently induce vasoconstriction/hemostasis during the liposuction procedure a minimum of 500 mL of tumescent fluid must be used.
6. After approximately 10 minutes, the adipose tissue is harvested through the same incision, using the aspiration cannula attached to the Toomey syringe
7. After the syringe is filled (complete filling is not required), cap syringe and replace with empty one
8. Continue fat harvest until desired volume is safely achieved, with the target volume of adipose tissue harvested limited to approximately 450 mL
9. Fat harvest will be limited to areas where tumescent fluid has been infiltrated
10. Vital signs are monitored continuously during liposuction procedure
11. Close surgical incision with appropriate suture
12. Apply pressure bandage immediately upon conclusion of tissue harvest

NOTE: Approximately 0.5 mL blood must be drawn and delivered to the unblinded staff prior to dose preparation. The blood will be used to prepare the fat alone control (see [Section 7.2](#)).

#### ***9.3.1.3 – Fat Harvest Stopping Rules***

The physician performing the fat harvest procedure should continuously monitor the patient for signs of significant bleeding from the puncture site(s) and overall hemodynamic stability. The liposuction procedure should be terminated if any of the following occur:

1. Drop in systolic blood pressure < 90mm/Hg that is unresponsive to volume or pressor support
2. Profuse or uncontrollable bleeding from the puncture site(s)
3. Rapid expansion of subcutaneous space at the liposuction site(s) related to bleeding into the subcutaneous space
4. Hemoperitoneum or pneumoperitoneum
5. Hemothorax or pneumothorax
6. Evidence of perforation of a vascular structure that requires ligature or surgical control

## 7. Evidence of perforation into abdominal cavity, peritoneum or gastrointestinal organ

Should any of the above occur, the fat harvest procedure should be terminated and the patient treated according to standard of care. DO NOT PROCEED WITH INJECTION. Complete the study specific SAE form and notify the sponsor within 24 hours.

### **9.3.2 *Between Fat Harvest and ADRC Injection***

Vital signs will be monitored continuously between the fat harvest and cell injection procedures.

### **9.3.3 *Fat + ADRC Injection***

The following procedure is recommended for subcutaneous injection into the scalp for the treatment of baldness due to alopecia androgenetica:

#### Autologous Fat & Saline Injection

This fat or saline injection procedure will occur after the completion of the liposuction. Aseptic technique should be maintained throughout the procedure. A treatment grid will be prepared in the area to be treated. The grid is a piece of silicone rubber that is placed on the scalp of the subject in the desired position and a surgical skin marker is used to mark each of the holes which are spaced every centimeter. The recipient site is anesthetized using a local ring block with 1% lidocaine with 1:100,000 epinephrine. Aliquots of 0.2mL should be injected in a circular ring fashion and the dosage should be adjusted according to the response of the patient and the site of administration. The lowest concentration and the smallest dose producing the required effect should be given. The maximum dose delivered should not exceed 7mg/kg. Sedation may be employed to minimize patient discomfort at the discretion of the investigator. Tissue from the Puregraft 50 is prepared in separate, sterile 1mL luer lock syringes, and an 11-blade scalpel can be used to make a stab incision (incision is made at a strategic insertion point to facilitate access to the area to be treated) to allow insertion of a 0.9mm-1.2mm diameter blunt-tip cannula. This cannula is then inserted into the subcutaneous adipose tissue plane and the tip is fanned into each 1 square centimeter grid to deliver 0.1mL of tissue or saline (no-fat control).

#### ADRC & Saline Injection

After preparation of the ADRCs, either the low or high dose of ADRC or saline will be injected using a 25G needle directly through the skin into the layer of subcutaneous adipose using the identical grid markings made in the paragraph described above. Additional local anesthesia ± sedation may be applied as deemed necessary by the investigator.

A summary of the clinical workflow is described in [Appendix C](#).

## **9.4 Immediately Post-Injection (Day 1)**

- Vital Signs will be monitored for one hour following the injection procedure
- HGB/HCT blood level will be evaluated

- Assessment of injection and fat harvest site
- Overall physical assessment

### **9.5 Post-injection Follow-up visits (Week 1)**

- Physical examination
- Vital Signs
- Assessment for Adverse Events

### **9.6 Post-injection Follow-up visits (Weeks 6, 12, 24, and 52)**

- Physical examination
- Vital Signs
- Assessment for Adverse Events

The following tests are to be performed:

- Subject questionnaire
- Global photography
- Hair Investigator Satisfaction Survey

A summary table of all follow up evaluations is outlined in [Appendix B: Schedule of Procedures](#)

### **9.7 Early Termination Evaluation**

Subjects that discontinue early from the study, unless consent is withdrawn, shall have an Early Termination (ET) evaluation. This visit shall take place as soon as possible after it is determined that the Subject will be withdrawn from the study.

If the ET Visit occurs prior to the Week 24 visit the observations and procedures for the ET Visit are the same as those required at the Week 24.

The reason for early withdrawal must always be clearly documented in the Subject's source documentation. Contact with the Subject must be attempted to determine overall health status, and contact details must be documented in the Subject's source documentation. If lost to follow-up, details of three contact attempts must be documented in the Subject source documentation and every effort must be made to determine if the Subject has expired.

## 10 RISK/BENEFIT ANALYSIS

### 10.1 Risks

The use of adult regenerative cells from adipose tissue and other sources has shown improvement in muscular (cardiac) function after injection into ischemic areas of the heart. The PRECISE Clinical Trial has shown an acceptable safety profile and signs of benefits following intramyocardial administration of ADRCs processed by the Celution System. Every potential complication of ADRC injections are unknown at this time; however injection of cells from adipose tissue have been delivered with guided intramyocardial injections with no clinical significant sequelae. A clinical trial of 12 patients with hand dysfunction and pain from scleroderma followed for 6 months showed minor adverse events related to subcutaneous injection, typical liposuction adverse events, and no adverse events directly related to ADRCs.

#### 10.1.1 *Subcutaneous Delivery Risk Analysis*

Risks involved with subcutaneous delivered adipose plus cells include:

- Hematoma or bleeding
- Infection
- Inflammation, rash, or papules at the injection site
- Nerve injury, pain, paresthesias or sensory disturbances
- Diminished function
- Shock loss

Direct intramuscular injections of Celase has been carried out in rodent models showing a margin of safety of greater than 10 for injection of Celase into the heart muscle. In addition, intra-ventricular applications of ADRCs into rat hearts during efficacy studies did not result in adverse events over 12 weeks of follow-up. Further, as noted above, 21 patients treated by direct injection into the muscle of the heart in the course of the PRECISE study exhibited no adverse events associated with ADRC injection. In addition, a study of 12 patients with subcutaneous injection in the fingers of patients with scleroderma showed minor adverse events and no serious adverse events.

#### 10.1.2 *Subcutaneous Injection Risk Management*

Investigators and all study personnel will be trained in the details of all aspects of the study procedures. To minimize risks and increase the chances of a favorable clinical outcome the following measures are required:

- Enrollment of Subjects who qualify per the inclusion/exclusion criteria in the protocol
- Strict adherence to the study protocol
- Use sterile technique throughout the procedure
- Use standard of care for the monitoring of and treatment of possible adverse events following injection procedure

### ***10.1.3 Celution & Puregraft System Risk Analysis***

The investigators and all study personnel will be trained in the details of all aspects of the study procedures relevant to their particular area of responsibility.

- Train investigators and all study personnel in the details of the operation of the Celution & Puregraft System.
- Inspect the package integrity and sterility indicators on all disposables used with the devices and maintain sterility of the fluid paths.
- Follow Instructions for Use for the Celution & Puregraft Systems, including all warnings, precautions and contraindications.

